### Background and Significance

Recent research has provided new information regarding relative risks, common mistakes, as well as low compliance rates for a variety of occupant protection recommendations. Thus, this is an ideal time to re-examine the National Highway Traffic Safety Administration's (NHTSA) approach when presenting child passenger safety (CPS) recommendations and assess various methods of framing the information, as well as the scope of the information provided. Age-appropriate restraints and rear seating dramatically reduce injury in a collision (Arbogast, Jermakian, Kallan, & Durbin, 2009; Durbin, Chen, Smith, Elliott, & Winston, 2005; National Highway Traffic Safety Administration, 2010; Rice & Anderson, 2009). Yet, at every step in the recommendations, advocates struggle with a "hard sell"—keeping children maximally protected for the longest time possible. Indeed, the primary reasons for injuries to children who are restrained at the time of motor vehicle crashes relate to prematurely turning a child forward, premature graduation from harnessed safety seats to booster seats, premature graduation from booster seats to adult safety belts, misuse of safety restraints and seat belts, and children seated in the front seat of the vehicle (Arbogast et al., 2009; Durbin et al., 2005; Henary et al., 2007; Lennon, Siskind, & Haworth, 2008; Rice & Anderson, 2009). Compared to appropriately restrained children, unrestrained children are greater than 3 times more likely to sustain injury in a crash, and children traveling in *inappropriate* restraints for their size are at 2 times the risk of injury (Durbin et al., 2005). Rear seating offers independent and additive safety protections in a crash (Durbin et al., 2005; Lennon et al., 2008).

In March 2011, NHTSA revised its CPS recommendations. The new guidelines are categorized by age rather than by type of child seat in order to keep pace with the latest scientific and medical research and the development of new child restraint technologies. The recommendations are supported by many new products which accommodate higher weights for children in each type of child restraint (rear-facing only, convertible, booster). For example, research supports that infants are safer travelling rear-facing versus forward facing (Durbin et al., 2005). The new guidelines are also consistent with the latest advice from the American Academy of Pediatrics. Both organizations' recommendations highlight that there is no need to hurry to transition a child to the next restraint type.

A possible modification to presenting the recommendations includes the addition of information regarding installation tips. Misuse of safety restraints is common (at least 73%) and is not limited to traditional safety seats (Arbogast & Jermakian, 2007; Decina & Lococo, 2005; Dukehart, Walker, Lococo, Decina, & Staplin, 2007; Garcia-Espana & Durbin, 2008; O'Neil, Daniels, Talty, & Bull, 2009). Proper use of a restraint is vital for maximum protection, yet the added effectiveness of providing installation tips with the recommendations is not known and should be evaluated.

From a risk communication perspective, it is also rather striking that the current recommendations do not explain the safety rationale behind the advice. Parental understanding of the reasons for each recommendation is central to communicating the vulnerabilities of children and

the additional risk exposure that comes with inappropriate restraint. Perceptions of risk and recognition of personal (or familial) vulnerability are key determinants of behavior change and can override parents' comfort level with following the (often unsafe) societal norm (Bandura, 1986; Slovic, 1991; Weinstein, 1988). Societal norms and their influence are also worth examining. Normative feedback interventions (often used in alcohol research) capitalize on the consistent finding that members of the public adjust their own levels of risk exposure to match the societal norm (Walters & Neighbors, 2005). Social norms feedback approaches are typically used when the base percent *safe* rate in the population is *high* (Marlatt et al., 1998; Miller, Rollnick, & Conforti, 2002). Normative information about CPS misuse and noncompliance is often communicated to parents, yet it may be contraindicated because in many cases the societal norm is one of low compliance. Thus, in addition to modifications to posing/presenting the CPS recommendations to ensure they evolve with the state of the science and evidence from the field, this study provides an important opportunity to empirically examine the relative benefits or detriments of additional information provided with the recommendations.

## Research Overview

The purpose of this research is to assess various methods of framing NHTSA's CPS recommendations, as well as the scope of the information provided. This project will conduct two experimental studies. Data will be collected from parent participants in two large metropolitan statistical areas on the east coast of the United States. In the first study, participants (N= 300) will be randomized into one of five groups to examine relative effectiveness of, and parent preferences for, different methods of framing CPS recommendations. That is, the goal of the first study is to determine HOW to best communicate the recommendations to parents (e.g., should we include information regarding risk- reduction/rationale, should we emphasize the "hardest sell" for advocates over all other information, etc.). In the second study, participants (N= 240) will be randomized into one of four groups to examine the relative effectiveness of CPS recommendations delivered in combination with other types of information. That is, the goal of the second study is to determine the type and amount of EXTRA information to include in the recommendations without losing the clarity and power of the key recommendations (e.g., normative information is often included but theoretically is contra-indicated, installation information is not included but theoretically may be necessary, etc.). It is hoped that the findings of this research inform the development of more effective ways to communicate messages for child passenger safety. These studies and their methods are explained in detail in the sections that follow.

## Study 1 Methods

### *Study Design*

For Study 1, a 5 (CPS Recommendation Version) X 2 (Time) experiment will use a randomized controlled trial design to examine relative effectiveness of and parent preferences for different methods of framing child passenger safety recommendations. As described in more detail below, parent participants will be electronically randomized to one of five groups (including four experimental conditions and one control group), and will respond to pre-post surveys.

### *Sampling Plan*

The geographic regions in which the study will take place include two large Metropolitan

Statistical Areas (MSAs): Philadelphia – Camden – Wilmington (Delaware Valley) and Virginia Beach – Norfolk – Newport News (Hampton Roads). The Delaware Valley MSA includes 13 counties in four States with a population of over 5.9 million people. The Hampton Roads MSA includes 10 cities and six counties in two States (VA-NC), with a population of over 1.6 million. These are two socio-economical and culturally diverse areas that range from the rural areas of VA's Eastern Shore and PA's farming communities, to large concentrations of people living in urban and suburban settings.

The sample will include 300 parents of children ages 0-12 years. Although expected to be a convenience sample, efforts will be made during recruitment and screening of participants to ensure that the sample under study is representative of the larger population, and that the study includes a variety of income levels, education levels, and racial/ethnic groups (at least Black, White, Latino) across the study conditions.

Power analysis indicated that a sample of 196 participants is adequate to detect small effect sizes above Cohen's  $d = 0.25$  with a statistical power of 0.80 at the standard significance level of  $\alpha = .05$ . Equal variance between groups is expected due to random assignment. Effect sizes for similar studies of intervention messages with smaller sample sizes and fewer experimental groups have been in the medium to large range (Cohen's  $d = .50$  to 1.68) (Will, Sabo, & Porter, 2009). Therefore, the sample size of 300 participants will be ample to detect group differences in this study.

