### ***Data Analysis Plan***

Data analysis will determine which CPS recommendation version produces the maximum desired outcome (e.g., correct CPS restraint selection, increased knowledge of restraints, enhanced perceptions of efficacy and risk). Data analysis will begin with data cleaning such as checking for missing data and outliers and ensuring normality and linearity of all dependent variables. Next, bivariate correlations will be conducted on all dependent variables to assess their relation to each other and to determine the type of inferential statistics to conduct. Specifically, if dependent variables are moderately inter-correlated, then a 2 (Time) x 5 (CPS Recommendation Version) MANOVA with follow-ups, post-hoc test for group, and simple effects analyses (if the interaction is significant) will be conducted. If dependent variables exhibit inter-correlations near zero or are highly inter-correlated, then multiple 2 (Time) x 5 (CPS Recommendation Version) ANOVAs with post-hoc test for group and simple effects analyses (if the interaction is significant) will be conducted. In the event that the data are found to violate the assumptions of normality that are necessary for parametric tests, data transformations to improve normality or appropriate nonparametric tests, such as the Friedman test and follow-up Multiple Comparison Tests, will be performed instead. Additionally, the study team may conduct several secondary analyses, including a multiple regression for CPS restraint selection to determine which CPS recommendation version best predicts correct restraint selection. Also, variables such as perceived relevance and accuracy of CPS information, age, sex, race, education, income, number of children, and ages of children may be used as covariates to eliminate potential confounding variables and better explain variance in the analyses. The results of Study 1 will be written into a brief research report for NHTSA. No reports or presentations will identify individual participants.

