### ***Sampling Plan***

Participants for Study 2 will be drawn from the same two broad geographic regions (Delaware Valley MSA and Hampton Roads MSA) as Study 1, with the same procedures followed for assurance of representativeness of the convenience sample. The sample will include 240 parents of children ages 0-12 years. An added exclusion criterion for Study 2 will be that the participants cannot have participated in Study 1.

Power analysis indicated that a sample of 179 participants is adequate to detect small effect sizes above Cohen's  $d = 0.25$  with a statistical power of 0.80 at the standard significance level of  $\alpha = .05$ . Equal variance between groups is expected due to random assignment. Effect sizes for similar studies of intervention messages with smaller sample sizes and fewer experimental groups have been in the medium to large range (Cohen's  $d = .50$  to 1.68) (Will, Sabo, & Porter, 2009). Therefore, the sample size of 240 participants will be ample to detect group differences in this study.

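### Both sample-size statements claim 80% power for a small difference (Cohen's d = 0.25), but 196 and 179 are the sizes for a medium omnibus effect (f = 0.25)

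*Protocol*

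**What the plan says.** Protocol, Study 1 Methods, Sampling Plan: "a sample of 196 participants is adequate to detect small effect sizes above" a d of 0.25. Power is given as 0.80 and alpha as .05. Study 2 Methods, Sampling Plan, makes the same statement with a different total: "a sample of 179 participants is adequate to detect small effect sizes above" a d of 0.25, at the same power and alpha. Both sections name the metric as Cohen's d.

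Each section then cites earlier message studies "with smaller sample sizes and fewer experimental groups have been in the medium to large range" (d = .50 to 1.68) and concludes, for Study 1, that "the sample size of 300 participants will be ample to detect group differences in this study". Study 2 draws the same conclusion for 240.

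Study 1 has five arms: "parent participants will be electronically randomized to one of five groups (including four experimental conditions and one control group"). Study 2 has four. Equal allocation gives 60 per arm in both. The Data Analysis Plan for Study 1 uses a two-by-five MANOVA or, failing that, a set of univariate analyses: "CPS Recommendation Version) ANOVAs with post-hoc test for group and simple effects analyses (if the interaction is significant) will be conducted". Study 2 has the two-by-four equivalent.

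The power statements name no test, give no pre-post correlation and do not mention Cohen's f.

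**The concern.** Cohen's d is a standardised difference between two groups. If d = 0.25 is meant as written, 196 parents over five arms (about 39 each) or 179 over four (about 45 each) are far too few for 80% power. The required total also falls when there are four arms instead of five. An omnibus F test behaves that way. A fixed per-arm requirement for one pairwise comparison would give totals in the ratio 5:4, and 196:179 is not that. This suggests that 0.25 entered the calculation on another scale.

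The studies are meant to find which version, or which combination of information, does best, and the planned post-hoc tests compare arms. Four of the five Study 1 arms are versions of the same recommendations, and all four Study 2 arms contain the same core recommendations, so true differences may well be small. A reader who believes that small differences are covered could take a non-significant result as evidence that the versions are interchangeable.

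**Working it through.** **Inputs (Protocol, Study Design and Sampling Plan of each study).** Study 1: k = 5 arms, stated requirement 196, planned N = 300. Study 2: k = 4, stated requirement 179, planned N = 240. Alpha .05, power .80, effect 0.25. Tests are taken as two-sided, which the protocol does not state.

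**1. Reproducing the stated totals.** For the one-way omnibus F test, power = P(F′ > F₀.₉₅; k−1, N−k, λ), with F′ noncentral F and λ = N f². With f = 0.25, λ = 0.0625 N.

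| k | N | λ | Power |
|---|---|---|---|
| 5 | 195 | 12.19 | .798 |
| 5 | **196** | 12.25 | **.8005** |
| 4 | 178 | 11.13 | .799 |
| 4 | **179** | 11.19 | **.8015** |

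Both stated figures are the exact minimum.

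**2. The other route to the same totals.** For a time-by-group interaction with m = 2 occasions and pre-post correlation r, λ = N f² m/(1−r). With f = 0.125 and r = 0.5, λ = N × 0.015625 × 2/0.5 = 0.0625 N, with the same degrees of freedom, so the totals are again 196 and 179. With two occasions the arm's interaction effect is half its deviation in mean change. An f of 0.125 therefore means that mean changes have an SD across arms of 0.25σ, the same spread as in step 1.

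**3. What that spread means between arms.** With an SD of arm means of 0.25σ, the distance between the most extreme arms is:
- k = 5: from 2 × 0.25 × 5/√24 = 0.51 SD to 0.25 × √10 = 0.79 SD.
- k = 4: from 2 × 0.25 = 0.50 SD to 0.25 × √8 = 0.71 SD.

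The protocol itself puts d = .50 at the start of the medium range.

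**4. What d = 0.25 needs.** By the normal approximation, n per arm = 2(1.960 + 0.842)²/0.25² ≈ 252; the exact t test gives 253. Totals with unadjusted tests are 5 × 253 = 1,265 and 4 × 253 = 1,012. With Tukey's all-pairs adjustment they are about 2,045 and 1,492.

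**5. Power for d = 0.25.**

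| Comparison | Study 1 | Study 2 |
|---|---|---|
| Pairwise, unadjusted, at the stated 196 / 179 | 19% | 22% |
| Pairwise, unadjusted, 60 per arm | 27% | 27% |
| Pairwise, Tukey, 60 per arm | 9% | 11% |
| Omnibus at planned N, extreme arms 0.25 SD apart | 16–35% | 18–33% |

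The 27% holds for posttest scores alone and also for change scores with r = 0.5, because the variance of change is then 2(1−0.5)σ² = σ². The omnibus ranges cover the possible positions of the other arms: f = 0.079–0.122 for k = 5 and 0.088–0.125 for k = 4. With ANCOVA on the pretest score, the unadjusted pairwise power rises to 35% at r = 0.5 and 62% at r = 0.8.

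**6. What the planned samples do support.** Omnibus power for f = 0.25 is 95% at N = 300 and 91% at N = 240. At 60 per arm, the pairwise difference detectable with 80% power is d ≈ 0.52 unadjusted, and 0.66 (Study 1) or 0.63 (Study 2) with Tukey. At d = 0.50, the bottom of the cited range, pairwise power is 78% unadjusted, and 50% (Study 1) or 56% (Study 2) with Tukey.

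**The case against.** The strongest reply has four parts.

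- **The f-for-d mislabel is inferred.** The protocol never writes f, and the interaction route suits the planned pre-post design better. Under the usual conversion d = 2f, f = 0.125 is d = 0.25, so the label may have come from there. This stands as a caution about the origin of the error. It does not save the statement, because that conversion describes two groups, and with four or five arms the implied spread still puts the extreme arms at least 0.50 SD apart.
- **The sentence calling the sample ample follows the cited effects of d = .50 to 1.68.** It promises detection of group differences, not expressly small ones. That is a fair reading. But it also follows a claim about small effects, and at d = 0.50 the adjusted pairwise power is only 50% or 56%.
- **Baseline information may help.** The same instruments are used twice in one session, and the pre-post correlation could be high. Unadjusted pairwise power for d = 0.25 does reach 80%, but only at r ≈ 0.87 (ANCOVA) or 0.88 (change scores). In Study 2 the arms form a 2 × 2 layout. A pooled 120 v 120 contrast has 49% power without adjustment and about 80% with adjustment at r ≈ 0.73. The protocol assumes no such correlation and plans a 2 × 4 analysis.
- **Nowhere does the protocol say that a null result will be read as equivalence.** That is true. The risk lies in how a report will be read, not in a stated rule.

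Tukey is only illustrative here, since the protocol does not name its post-hoc test.

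**Conclusion.** The concern holds for both studies. As written, 80% power for small effects from d = 0.25 upward is wrong. The totals 196 and 179 correspond to a medium omnibus effect, and this does not depend on which of the two routes produced them. At the planned 60 per arm, a pairwise d = 0.25 has 27% power unadjusted and about 10% with an all-pairs adjustment, and a study with 80% power for it would need roughly four times the planned number (253/60 ≈ 4.2), or more with adjustment.

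These figures assume equal allocation, 60 analysed per arm, two-sided tests at .05, and posttest scores or change scores with r = 0.5 unless another value is given. Excluding participants who go through the screens too fast, as the protocol plans, would lower them. Only a pre-post correlation near 0.87, which the protocol does not claim, would bring the unadjusted pairwise test to 80%.

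The sample sizes themselves can be defended for a medium omnibus effect. The fault is in what the protocol says they can detect.

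**What to change.** Keep N = 300 and N = 240, and rewrite both Sampling Plan statements.

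1. State the test, the effect metric (f or d) and any pre-post correlation that the calculation used. The sponsor should confirm which calculation was run.
2. Replace the description of the effect as small with medium, and remove the conclusion that the samples are ample.
3. Give the sensitivity at the planned size. If the omnibus calculation is confirmed, suitable wording is: *A total of 196 (Study 2: 179) gives 80% power for an omnibus effect of Cohen's f = 0.25, a medium effect. With 60 analysed per arm, power for f = 0.25 is 95% (91%). Pairwise differences of about d = 0.52 without adjustment, or 0.66 (0.63) with Tukey's adjustment, are detectable with 80% power.* If another post-hoc test is intended, replace the Tukey figures with those for that test.
4. Add that a non-significant difference between versions will not be read as equivalence.

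The cost is wording only, with no extra participants and no change of procedure. The stated sensitivity becomes less favourable.

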### ***Recruitment***

The study team will work with a variety of colleagues in each geographic locale to disseminate the study recruitment announcement (see recruitment flyer) through their email listserves, social media, office flyer postings, and personal contacts. Colleagues assisting with recruitment represent agencies such as Safe Kids USA, Places and Programs for Children, Consortium for Infant and Child Health, etc. Through these contacts, we anticipate reaching vast networks of agencies and professionals that directly serve a diverse parent community. The team has used similar methods in the past for successful recruitment activities.

Interested participants will call the phone number on the recruitment materials (an email address will also be an option), at which point a member of the study team will briefly describe what is involved in participation, will ask some demographic questions, and will ask whether or not the participant is comfortable reading English-language text displayed on a computer screen (see phone script). For qualifying participants, a study appointment will be scheduled. Preliminary demographic questions (e.g., age, age of children, etc.) will be asked to ensure the participant is appropriate for the study and help the study team ensure equitable assignment within the randomization schedule across conditions. Enrolled participants will receive compensation (e.g., retail store gift card) following participation in this study, which is expected to take approximately 60 to 75 minutes.

[figure not shown]
### ***Procedure for Participation***

Enrolled participants will be asked to arrive at a designated computer lab/center (university lab or commercial learning center) at their appointment time to participate in the study. This study will use a secure web-based study protocol in which participants will view a series of user-friendly screens that will automatically lead them through the informed consent document (detailing the logistics of the study, the study's duration, their rights as a participant, and remuneration for their

participation), pretest measures, study materials specific to condition assignment (described separately below), and post-test measures at the participant's pace. (See Flow Diagram for Study 1.)

Contrary to past decades, computerized surveys and study presentations are now a valid and reliable means of collecting representative research data, as 79% of US adults under age 65 use the internet (Pew Research Center, 2011). Moreover, a study assistant will be present at the computer center to assign participants to a computer station, help participants log into the study using a secure code, orient them to the process of completing study materials, and answer any questions as they arise. Participants will complete study materials individually, but we are expecting to be able to run as many as 25 subjects simultaneously at different computers in the computer lab/center.

Flow Diagram – Study 1

As participants respond to survey questions, they will simply check off their desired response(s) in the same manner as they would on paper. Manipulation checks (e.g., page and survey view times) will be electronically embedded to ensure that participants attend to the messages and read questions versus randomly choosing answer choices; data from participants who forwarded through screens too quickly to have read them will be excluded from the dataset. The data collected from all participants will be anonymous, and no person's name or other personal identifier will be stored with the data (a coding process will be used to link pre-post data that does not identify the participant). The software package used to collect the web-based survey data (e.g., Inquisite) will automatically send the survey responses to a securely housed and password-protected statistical database (with individual cases for participants and separate variables for each data element) for later analysis with SPSS statistical software. The test messages and survey instruments will be developed on a Windows 2008 Server. The user interface will be designed to provide ease of use and data integrity. Coding will be done in ASP.Net and Java Script. The data will be stored securely on a Microsoft SQL database. Biweekly quality controls will be conducted to ensure that data are being collected and coded appropriately. Once all data have been collected, the Eastern Virginia Medical School (EVMS) research team will perform data analysis and archival tasks.

